5. TRIAL DESIGN

5.1 Primary endpoint

Variables for the evaluation of safety and feasibility:

- 1) Injection site reactions, skin reactions 1 hour post injection vs. before injection.
- 2) Occurrence of AEs, continuously registered and status summarized at 5 and 12 months after the first injection.
- 3) Laboratory measurements (hematology and clinical chemistry), status summarized at 5 and 12 months after the first injection vs. baseline.
- 4) Physical examinations, including neurological assessments, status summarized at 5 and 12 months after the first injection vs. baseline.
- 5) GAD65A titer in serum, levels at 5 and 12 months after the first injection vs. baseline.
- 6) Vital signs (blood pressure), status summarized at 5 and 12 months after the first injection vs. baseline.

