5.4 Time line and main study events

The project is expected to take 2 years. Given that LADA patients constitute 10% of the total diabetes population, our expectation is that the study could be fully recruited within 1 year. Each patient will then be followed for 12 months. Study close out, data cleaning and analysis, compilation of final report, etc. will take place during the final 6 months of the project. The schedule of the main study events is given in Table 1. The end of the trial is defined as the last visit of the last patient included in the trial and the time point where all data have been collected.

Table 1: Schedule of main events for the trial

Event	V1 Screening	V2		V3 Baseline		V4 ^a M1	V5 ^a M2		V6 M5		V7 M12	
		-44 to -60	-31	-30	1	2 (+2)	30 (±5)		150 (±14)	151 (+2)	360 (±14)	361 (+2)
DAY	-44 to -60	-31	-30	1	2 (+2)	30 (±5)	60 (±5)	90	150 (±14)	151 (+2)	360 (±14)	361 (+2)
Informed consent	X	X										
Demographics	X											
GAD-alum (4 µg) a, b, c,					X	X	X					
Vitamin D ^d start /end			Start					Stop				
Neurological assessment	X			X		X	X		X		X	
Concomitant medication	X			X		X	X		X		X	
Vital signs (BP)	X			X		X	X		X		X	
Injection site inspection; investigator/study nurse ^e					X	X	X					
AEs				X		X	X		X		X	
Glucagon test ^{c,f}			X		X					X		X
MMTT ^f		X		X					X		X	
Blood and urine sampling for safety, genetics, vitamin D levels and immunology:												
Hematology	X			X		X	X		X		X	
Clinical Chemistry	X			X		X	X		X		X	
GAD65A titer^g	X			X		X	X		X		X	
HLA characterization				X								
Vitamin D level	X	X		X		X	X		X		X	
Other immunological parameters^h		X		X		X	X		X		X	
Creatinine	X			X		X	X		X		X	
Blood sampling for diabetes status:												
Fasting C-peptide	X	X	X	X	X	X	X		X	X	X	X
Fasting glucose	X	X	X	X	X	X	X		X	X	X	X
Glucagon stimulated C- peptide and glucose			X		X					X		X
MMTT stimulated C-peptide		X		X					X		X	
MMTT stimulated glucose		X		X					X		X	
HbA1c	X	X		X		X	X		X		X	

[Abbreviations for Table 1: V= visit; M=month; GAD= Glutamic Acid Decarboxylase; BP=Blood Pressure; AEs=Adverse Events; MMTT=Mixed Meal Tolerance Test; GAD65A=Glutamic Acid Decarboxylase Antibodies; HLA=Human Leukocyte Antigen; HbA1c=Hemoglobin A1c]

- a. Study drug administration: For visit 4 and 5 the visit date must be set in accordance with visit 3 and 4, respectively, so that the first, second and third doses will be 30 days apart (\pm 5days).

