- b. The GAD-alum injection directly into the inguinal lymph node is to be done by an appropriately qualified radiologist at the X-ray department at the study site by help of ultrasound technique.
- c. On day two at visit 2, the glucagon test needs to be done before the injection of GAD-alum.
- d. Supplementation with vitamin D starts at day -30, after the glucagon test has been performed, if the vitamin D serum levels are below 100 nmol/L (40 ng/ml) at screening. If the patient has vitamin D serum levels above 100 nmol/L (40 ng/ml) at screening, no Vitamin D supplementation will be given for that patient.
- e. The investigator/study nurse will inspect the injection site before and after the injection is given and record any injection site reactions in the Case Report Form (CRF).
- f. The MMTT and the Glucagon test must be carried out on separate days, as each test has to be performed in the fasting state.
- g. Antibodies against IA-2 (islet cell antigen 2), ZnT8 (Zink transporter 8) and insulin will be measured at Baseline and at Visit 7.
- h. Antibodies against SARS-CoV-2 will be measured at Visit 6 and Visit 7.

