8.2 Methods for the recording of effect parameters

The patient must attend all study visits in the morning following an overnight fast (>10 hours, water allowed). Each visit should be completed as scheduled (see Table 1). However, for patients with evidence of an infection, the visit should be postponed until the patient has recovered.

8.2.1 *Endogenous insulin production: Visit 2, 3, 6 and 7*

The MMTT [37] and the GSCT [36] must be performed according to the instructions in the specific laboratory manuals. The tests must be carried out on separate days, as each test has to be performed in the fasting state. Also, if the patient develops need for insulin treatment during the study period, the patient must not take short acting/direct acting insulin within 6 hours before the test. The patient is allowed to take base-insulin the day/night before, but not in the test morning and during the MMTT and the GSCT. If the patient does not fulfill the above mentioned criteria, the MMTT and GSCT should be rescheduled and the patient return to the study site within 5 days if possible.

MMTT: The patient will be given a standardized liquid nutrition mixture. Blood samples will be secured for glucose and C-peptide measurements at before and 0, 30, 60, 90 and 120 (± 5) minutes after the meal.

GSCT: The patient will receive an intravenous injection of 0.5 mg glucagon. Blood samples will be secured both before and 6 minutes after the injection for the measurements of glucagon-stimulated C-peptide and glucose.

8.2.2 *Immunological tests: Blood samples collected at all visits: Visit 2-7*

Measurements of GADA titer and some of the relevant immunological parameters will be performed at the Department of Clinical and Molecular Medicine, NTNU. Measurements of Anti-SARS-CoV-2 will be performed at Laboratoriemedisinsk klinikk, St Olavs Hospital, Trondheim, and at Karolinska Universitetslaboratoriet, Stockholm. HLA classification will be

performed at Oslo University Hospital Rikshospitalet, Department of Immunology and Transfusion medicine. Classification and analyses of T-cells and other relevant immunological tests will be performed at Linköping University Hospital.

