9.3 Relationship to study medication

Relationship to study medication will be assessed for the two treatments (Diamyd and Vitamin D) separately. AEs with a causal relationship assessment of Unlikely related, Possibly related and Probably related will be considered to be Adverse Reactions.

Not related: This category is applicable to those AEs which, after careful medical consideration at the time they are evaluated, are judged to be clearly and incontrovertibly due to extraneous causes (disease, environment, etc.) and do not meet the criteria for study medication relationship listed under remote, plausible or probable.

Unlikely related: Time relationship non-existent or doubtful and/or other factor(s) certain or probable to have been causative.

Possibly related: Time relationship exists. Other possible causative factor(s) may exist (e.g., concurrent disease or concomitant medication). Improvement on dechallenges or dose reduction may or may not have been seen.

Probably related: Time relationship exists. No other possible causative factor(s) may exist (not reasonably explained by the patient's known clinical state or concomitant medication). Improvement on dechallenges or dose reduction (if performed) has occurred. Recurrence of symptoms on rechallenge (if performed) has occurred. A specific laboratory investigation (if performed) has confirmed the relationship.

9.4 Reporting and follow up of adverse and serious adverse events (AE and SAE)

All AE must be recorded in the CRF, defining relationship to study medication, severity and seriousness. AE should also be recorded by the physician or study nurse in the patient file/notes.

Timelines and Reporting of SAE

All SAEs must be reported, whether or not considered attributable to the study drug on a separate SAE Report Form. SAEs will be reported from signing of informed consent.

TFS Trial Form Support AB (TFS) will be responsible for reporting all SAEs in accordance with ICH Good Clinical Practice (GCP) and local regulations. Diamyd and TFS will complete and sign a “Pharmacovigilance Working Agreement” agreement covering the safety reporting responsibilities in the study. This agreement will ensure the sponsor is directly informed of each SAE reported by the investigators.

In order to meet the specified reporting requirements investigators should adhere to the following process for recording and reporting SAEs.

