10. STATISTICS

10.1 Statistical analysis plan

In brief the following analyses are planned:

All continuous variables will have the following descriptive statistics displayed: Number of observations (n), mean value, standard deviation, minimum, median and maximum. All variables of a categorical nature will be displayed with frequencies and percentages. The tabulation of the descriptive statistics will be split by visit. Where appropriate, baseline (screening) descriptive statistics will also be included.

Demographic and other baseline characteristics will be presented using descriptive statistics (summary tables).

Variables. The AE/SAE data will be presented using a standardized tabulation of the frequency and incidence rate of all observed AE/SAEs. The frequencies and incidence rates are calculated on a per patient basis. Adverse events will be summarized by body system, causality and severity. Other safety data will be presented as descriptive statistics.

Data regarding immune response, beta cell function, AE and other data will be summarized descriptively.

Analyses of data will be performed after 5 and 12 months from baseline. Data from the BALAD study (see Section 3.3.1) will be used as a historical control for the evaluation of treatment-related effects on the evolution of beta cell function parameters between baseline and 5 and 12 months of intervention. We acknowledge that it is difficult to statistically compare data from BALAD as a historical control with data from this pilot study, as the participants in BALAD were randomized to active treatment. The comparison will still be valuable, primarily as a pointer for future research.

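### Glucagon-test events on the day of the first injection may be counted as GAD-alum Adverse Reactions in the causality summary, because section 9.3 has no procedure category and counts even Unlikely related events

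*Combined protocol and SAP*

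**What the plan says.** Section 5.1 item 2 makes AEs part of the primary endpoint: "Occurrence of AEs, continuously registered and status summarized at 5 and 12 months after the first injection". No causality condition is attached.

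Table 1 (section 5.4) marks GAD-alum on Days 2 (+2), 30 and 60, and the glucagon test on Days -30, 2 (+2), 151 and 361. Both rows carry footnote c: "On day two at visit 2, the glucagon test needs to be done before the injection of GAD-alum". Section 8.2.1 gives the route: "The patient will receive an intravenous injection of 0.5 mg glucagon". Section 7.1 leaves the time of day of the injection to the radiologist, and no interval after the test is set.

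Section 9.3 states: "Relationship to study medication will be assessed for the two treatments (Diamyd and Vitamin D) separately". It has four ratings. Three of them (Unlikely, Possibly and Probably related) make the event an Adverse Reaction; only Not related does not. Section 10.1 plans: "Adverse events will be summarized by body system, causality and severity".

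**The concern.** With one arm, no placebo and about 15 patients, the causality rating is the main planned means of attributing an event to GAD-alum. On the day of the first injection the patient also receives intravenous glucagon, which has no line of its own in the rating. An event caused by the test can then appear in the table as a GAD-alum reaction. Because injections 2 and 3 have no stimulation test, the result could look like a first-dose effect.

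Safety is the primary objective (section 4), and the absence of safety concerns is one of the conditions for the next trial (section 5.3). Section 3.4 reports no treatment-related events beyond mild, transient injection-site reactions, so even one or two systemic events attributed to GAD-alum would stand out.

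**Working it through.** The plan has no power or precision figure to reproduce; section 10.2 gives about 15 patients and no formal power analysis. The check is a reading of Table 1 against section 9.3, then a calculation for scale.

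**1. Where test and injection coincide (Table 1, cells read by column position)**

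| Row | Days marked |
|---|---|
| GAD-alum | 2 (+2), 30, 60 |
| Glucagon test | -30, 2 (+2), 151, 361 |
| MMTT | -31, 1, 150, 360 |
| AEs | 1, 30, 60, 150, 360 |

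The overlap is Day 2 (+2): one of three injections and one of four glucagon tests per patient. The column positions come from text extracted from a PDF, but footnote c supports them independently, since it orders the test before the injection within one day. It names visit 2, whereas Table 1 places Day 2 and the first injection at Visit 3.

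**2. How section 9.3 treats a glucagon-caused event on Day 2, rated for Diamyd**

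| Situation | Rating that fits | Adverse Reaction to GAD-alum? |
|---|---|---|
| Beyond dispute due to an outside cause | Not related | No |
| Starts after the test, before the injection | Not related if beyond dispute; otherwise Unlikely (no time relationship) | No / Yes |
| Starts after the injection; test thought the probable cause | Unlikely | Yes |
| Starts after the injection; the two cannot be separated | Possibly | Yes |

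The third row is the telling one. An investigator who correctly believes that the test probably caused the event has a rating that fits exactly, and the event still counts.

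**3. Would a procedure line alone be enough?** No. An event rated Probably related to the glucagon test and Unlikely related to Diamyd would remain a Diamyd Adverse Reaction under the present rule.

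**4. Does the plan separate the two causes in another way?** Section 10.1 splits descriptive tables by visit, but Visit 3 contains the Day 1 MMTT, the Day 2 test and the injection together. A within-patient contrast exists in the schedule: injections without a test (Days 30, 60) and tests without an injection (Days -30, 151, 361). No analysis uses it. Only the Day -30 test precedes both treatments, because vitamin D starts after it. The AE row marks none of the four glucagon days, although 5.1 calls for continuous registration and 9.1 for recording at every visit.

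**5. Scale.** The documents give no event rate for the glucagon test. Let p be an assumed probability per patient of a test-related event on Day 2, with n = 15:

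expected patients = 15p; P(at least one) = 1 - (1 - p)^15

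| Assumed p | Expected patients | (1 - p)^15 | P(at least one) |
|---|---|---|---|
| 5% | 0.75 | 0.463 | 0.537 |
| 10% | 1.5 | 0.206 | 0.794 |
| 20% | 3.0 | 0.035 | 0.965 |
| 30% | 4.5 | 0.005 | 0.995 |

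These are events open to misattribution, not events that must be misattributed.

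**The case against.** The strongest case against has five parts.

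- **The endpoint itself.** A reader might infer that the primary endpoint is distorted. The documents do not support this: 5.1 item 2 counts all AEs, so a glucagon event enters it under any rating. Only the causality split and the Adverse Reaction count can be affected. This stands in full.
- **Attribution is not automatic.** A reader might also infer that every Day 2 test event becomes a GAD-alum reaction. Not related is available, and an event that starts before the injection has no time relationship to GAD-alum. This stands as a limit: the right word is *may*. The bar for Not related is high, however, and the wording of Unlikely catches much of what falls short of it.
- **The rates are assumed.** This stands. The probabilities show scale and are not evidence that the problem will occur.
- **No decision rule depends on the count.** Section 5.3 sets no reaction-rate threshold, all data will be listed (6.4b), and in about 15 patients the listings can be inspected. This lowers the stakes. It does not make the summary table right, and listings help only if onset relative to the test and the injection is recorded, which the plan does not ask for.
- **The contrast is weak.** The exact 95% interval is 0 to 22% for 0/15 and 4 to 48% for 3/15; these overlap widely. The by-injection table can therefore be descriptive only, and it needs AE recording on the glucagon days.

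**Conclusion.** The concern holds in a limited form. The first injection shares its study day with an intravenous glucagon test, causality is rated for two products only, and Unlikely related events count as Adverse Reactions even when another cause is certain or probable. Glucagon-test events on that day may therefore be reported as GAD-alum Adverse Reactions in the section 10.1 causality summary. One of three injections is affected, and the total AE count of the primary endpoint is not.

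The size cannot be derived from the documents. On an assumed rate of 5% to 30% per patient, 0.75 to 4.5 of 15 patients would be expected to have an event open to misattribution. The conclusion rests on the column reading of Table 1, supported by footnote c, and on section 9.3 being applied as written. It is worth correcting because attribution of events matters to a single-arm safety trial and the correction is cheap.

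**What to change.** 1. **Section 9.3 and the AE form:** add a causality line for study procedures (glucagon test, MMTT) beside Diamyd and vitamin D. For Day 2, record AE onset time relative to the test and to the injection.
2. **Section 9.3, for the summary tables:** do not count as a Diamyd Adverse Reaction an AE rated Unlikely related to Diamyd because another factor is certain or probable, or show these events on a separate line.
3. **Section 10.1:** tabulate AEs by injection number (1, 2, 3) beside AEs with onset on the glucagon-only days (-30, 151, 361). Label it a descriptive contrast and note that only Day -30 precedes both treatments.
4. **Table 1:** reconcile the AE row, which marks no glucagon day, with continuous registration in 5.1. Reconcile visit 2 in footnote c with Visit 3 in the table.

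The cost is a few fields on the AE form, one more table and, if AEs are not already collected on the glucagon days, their recording there. Tests, their order and dosing do not change.

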3.3 Background and rational

3.3.1 *Urgent need for a treatment that counters autoimmunity in LADA*

Latent Autoimmune Diabetes in Adults (LADA) encompasses approximately 10% of phenotypic type 2 diabetic patients [1]. LADA patients are by definition not insulin dependent at diagnosis. However, very many of these patients experience a successive decline of their own insulin secretion, something that renders these patients insulin dependent within a few years. The demise of LADA patients' insulin-producing beta cells is due to an autoimmune process that is similar to the autoimmune process in type 1 diabetes. The speed of beta cell demise is coupled with high levels of type 1 diabetes-like antibodies, in particular to antibodies against glutamic acid decarboxylase (GADA), which likely reflect the intensity of the autoimmune process [2, 3].

There is strong evidence that demise in beta cell capacity to release insulin couples to deterioration of metabolic control and that such deterioration in turn leads to an increased risk for complications of diabetes with serious consequences in terms of morbidity and mortality [4, 5]. In addition, reports indicate that LADA patients have worse metabolic control than other types of diabetes when comparing mortality [6, 7]. Consequently, there is an urgent need for therapies that counteract the ongoing destruction of beta cells in LADA patients. LADA is – as indicated above – a very common form of diabetes; this underscores the need for a therapy that works.

Very few studies, only 10 clinical trials listed on clinicaltrials.gov, have specifically investigated the extent to which different types of treatment could influence the decline of beta cell function in LADA patients (Clinicaltrials.gov as of February 15th 2019). The scarcity of trials and the resulting lack of evidence for best treatment in LADA has led to large regional variations in treatment.

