4. TRIAL OBJECTIVES AND PURPOSE

The purpose of the trial is to evaluate the effects of 3 intra-nodal injections of GAD-alum, together with oral vitamin D supplementation, in a population of LADA patients with high GADA titers. Effects will be summarized at 5 and 12 months after the first injection.

- The primary objective is to evaluate safety and feasibility of this treatment regimen.
- Secondary objectives are to test if the treatment induces a strong GAD-specific immune response similar to what has previously been observed in type 1 diabetes patients and to test for indications of preservation of endogenous insulin production.

The pilot study will be performed in order to support the launch of a larger placebo controlled clinical trial in the LADA population.

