5.3 Trial description

The proposed study is an open label Phase IIa feasibility trial. It is a pilot study that does not include a placebo arm. The time course of beta cell function in the trial will be compared to that in our recent trial, BALAD (described in 3.3.1), as a historical control. A positive outcome (i.e. no safety concerns, a robust immunological response and a favorable time course of beta cell function compared to BALAD) will pave the way for a placebo-controlled phase III study.

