8. ASSESSMENT OF EFFICACY

8.1 Effect parameters

See also Section 5.2, secondary endpoints. Endogenous insulin production will be measured by glucagon- and mixed meal stimulation of C-peptide at baseline and after 5 and 12 months of intervention. Metabolic control will be evaluated by measurements of HbA1c and fasting glucose at all study visits. Immunological response will be assessed by measurements of GADA and the immunological parameters listed in Section 5.2. Blood samples for the assessment of immunological response will be collected at all study visits.

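### GADA titer has two roles and no rule for reading a change, and by-visit means and medians measure within-patient titer change less precisely than a log-scale fold change

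*Combined protocol and SAP*

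**What the plan says.** Section 5.1, under the heading "Variables for the evaluation of safety and feasibility", gives as item 5 "GAD65A titer in serum, levels at 5 and 12 months after the first injection vs. baseline". No direction, threshold or fold change is attached to it.

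Section 8.1, in the efficacy chapter, says "Immunological response will be assessed by measurements of GADA and the immunological parameters listed in Section 5.2". The immunological list in 5.2 (items 6 to 9) covers GAD65-specific IgG subclasses, cytokines, cell phenotyping and proliferation, but not total GADA titer.

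Section 4 states "Secondary objectives are to test if the treatment induces a strong GAD-specific immune response similar to what has previously been observed" in type 1 diabetes. Section 5.3 defines a positive outcome as "no safety concerns, a robust immunological response and a favorable time course of beta cell function compared to BALAD", and none of the three conditions is quantified.

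Section 3.3.1 says of GADA levels, "which likely reflect the intensity of the autoimmune process". Section 3.4 names a speeding-up of autoimmunity as a theoretical risk of GAD-alum. The criteria in 6.4 for terminating trial treatment name HbA1c, C-peptide, stiff person syndrome and neurological or behavioural effects; GADA is not among them.

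For all continuous variables, 10.1 plans "Number of observations (n), mean value, standard deviation, minimum, median and maximum", tabulated by visit. It names no transformation and no within-patient change. Inclusion criterion 5 requires a titer above 190 U/ml and sets no upper limit. Section 10.2 plans approximately 15 patients without a power calculation.

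**The concern.** The treatment injects GAD in order to provoke a GAD-specific response, so some movement in GADA is to be expected. The protocol gives grounds for reading a rise as the intended effect (sections 4 and 8.1) and grounds for reading it as unwelcome (3.3.1 and 3.4). It does not say how the two are to be told apart. The trial is open-label and has no placebo arm, so without a rule the reading would be settled after the data are seen. The result then feeds the decision on a placebo-controlled trial.

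The summary statistics add to the difficulty. Titers are typically right-skewed, and the quantity of interest is each patient's ratio to their own baseline. Separate means and medians at each visit discard the pairing. The mean is also sensitive to a single very high titer.

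**Working it through.** **Roles, side by side**

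| Place | Role given to GADA titer |
|---|---|
| 5.1, item 5 | Primary safety and feasibility variable |
| 5.2, items 6 to 9 | Not listed (IgG subclasses are) |
| 8.1 | One of several measures of immunological response |
| 6.4 | Not among the treatment-termination criteria |
| 5.3 | Could feed either the safety condition or the response condition |

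So 5.2 and 8.1 do not agree, and no section supplies a reading rule.

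**One large responder (exact arithmetic, illustrative)**

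There is no figure in the plan to reproduce. Take 15 patients with equal baseline titers, 14 of them unchanged and one rising k-fold.

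- Ratio of raw means = (14 + k)/15. For k = 20: 34/15 = 2.27.
- Geometric mean ratio = k^(1/15). For k = 20: 20^(1/15) = 1.22.
- The median is unchanged.

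For k = 5, 10 and 50 the ratio of means is 1.27, 1.60 and 4.27, against geometric mean ratios of 1.11, 1.17 and 1.30.

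**Sampling range when there is a real rise**

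From the documents: n = 15 and entry above 190 U/ml. Assumed, because the documents give no titer distribution: log-normal titers, true two-fold rise, SD of ln fold change 0.6, baseline ln-SD 0.5 to 1.2. Where the entry cutoff is applied, a median of 500 U/ml before truncation is also assumed.

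Geometric mean ratio, directly: 2 × exp(±1.96 × 0.6/√15) = 2 × exp(±0.304), that is 1.48 to 2.71. It does not depend on the baseline spread, because each patient serves as their own reference.

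The other two summaries come from simulation, shown here without truncation (centre, then 95% sampling range):

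| Baseline ln-SD | Ratio of visit medians | Ratio of visit means |
|---|---|---|
| 0.5 | 2.00 (1.28 to 3.12) | 2.34 (1.65 to 3.43) |
| 0.8 | 2.00 (1.20 to 3.34) | 2.32 (1.58 to 3.62) |
| 1.0 | 2.00 (1.15 to 3.48) | 2.31 (1.51 to 3.76) |
| 1.2 | 2.00 (1.10 to 3.62) | 2.29 (1.44 to 3.94) |

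Truncation at 190 U/ml changes little. At ln-SD 1.2 the ranges become 1.20 to 3.57 for medians (centre 2.07) and 1.49 to 3.83 for means (centre 2.30).

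Widths on the log scale, relative to the geometric mean ratio (2 × 0.304 = 0.607):

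- Medians: ln(3.12/1.28) = 0.891, or 1.5 times as wide, at ln-SD 0.5; ln(3.62/1.10) = 1.191, or 2.0 times, at 1.2.
- Means: ln(3.43/1.65) = 0.732, or 1.2 times, at 0.5; ln(3.94/1.44) = 1.006, or 1.7 times, at 1.2.

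The ratio of means is also centred too high. The arithmetic mean of a log-normal fold change is 2 × exp(0.6²/2) = 2.39, and the ratio of means in samples of 15 sits near 2.3.

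**Width of the interval that would be reported**

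With n = 15 the 95% CI for the geometric mean ratio is the estimate times or divided by exp(2.145 × SD/√15). This factor is 1.32, 1.39, 1.74 and 2.29 for an SD of ln fold change of 0.5, 0.6, 1.0 and 1.5.

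**The case against.** A reader might infer that one and the same rise satisfies the response condition in 5.3 and breaks the safety condition. The documents do not support this. No section calls a GADA rise a safety concern. The remark in 3.3.1 concerns the speed of beta cell loss in LADA generally, not titers induced by injected antigen, and 6.4 leaves GADA out of its termination criteria. Nor does any section make a titer rise sufficient for a robust response.

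A reader might also infer that the variable cannot be interpreted at all. That is too strong. A biomarker may properly serve both safety and pharmacodynamics. The response can be judged from subclasses, cytokines and cell assays without total titer, and the other five primary variables are available alongside it. What is missing is a stated rule.

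On scale, 10.1 is introduced as a brief outline, it does not rank the mean above the median, and the wording of item 5 does not exclude a ratio. The planned median recovers the centre of the effect, so its weakness is precision rather than bias. It would be tempting to present the comparison as lost power, but the plan is descriptive and contains no test or interval for GADA.

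Finally, moving item 5 out of 5.1 would have a cost: this is the first intranodal study in LADA, and speeding-up of autoimmunity is a named theoretical risk. These objections stand. They leave the disagreement between 5.2 and 8.1, the missing reading rule and the imprecise summary of change.

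**Conclusion.** The point holds in a limited form. GADA titer is listed only as a safety variable, is used elsewhere as one of several response measures, and has no rule for reading a change. A rise could therefore be argued for or against a positive outcome. Separately, the by-visit summaries in 10.1 are a poor description of within-patient titer change. Under the assumed values, the range of plausible results is about 1.5 to 2.0 times as wide on the log scale for visit medians, and 1.2 to 1.7 times for visit means, as for the geometric mean ratio. The means also overstate a two-fold rise as about 2.3-fold.

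Every SD and fold change here is assumed. The size of the gain depends on the true spread of baseline titers and of individual responses. The consequence is an ambiguous and less precise input to the decision on a further trial, not an inflated error rate.

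**What to change.** - **10.1:** for GADA titer and the GAD65-specific IgG subclasses, report within-patient fold change from V3 to V6 and to V7, analysed on the log scale, as a geometric mean ratio with 95% CI plus individual profiles. Keep the planned median and range. Name V3 as the reference, because titer is also measured at screening and 10.1 puts screening in brackets after baseline.
- **5.1 and 5.2:** keep item 5 in 5.1, and also list total GADA titer among the immunological variables in 5.2 so that the list agrees with 8.1.
- **Reading rule:** state that, for safety, a change in titer is interpreted together with the harm signals the protocol already names (C-peptide, HbA1c and neurological findings). This governs interpretation of results and does not alter the treatment criteria in 6.4.
- **Cytokines:** use the log scale only with a stated handling of values below detection.

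The cost is wording in 5.1, 5.2 and 10.1. Table 1 already schedules titer and other immunological sampling at V3, V6 and V7, so no new data or visits are needed.
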